## SUMMARY

Introduction. Vitamin D regulates mineral metabolism, playing a crucial role in maintaining adequate bone density. Immunomodulatory, cardioprotective and

Version December 7th, 2015

antiproliferative effects have been described recently. Its deficiency has been associated with diabetes, cancer and increased mortality. 25OH vitamin D (25VD) is stable (with a half-life of over 2 weeks) and suitable for the evaluation of vitamin D sufficiency. It has been found that levels of 25VD are inversely related to those of the parathyroid hormone (iPTH), and its supplementation has been associated with a decrease in levels of iPTH in patients with Chronic Kidney Disease, although these results have not been uniform in patients on hemodialysis (HD). The usual treatment for secondary hyperparathyroidism in HD with active and analogous forms of vitamin D increases the risk of hyperphosphatemia and vascular calcifications.

The aim of the study is to evaluate whether cholecalciferol supplementation for a period of 12 weeks can normalize decreased levels of 25VD and reduce increased iPTH in HD patients with a vitamin D deficiency. Secondary aims: to evaluate decrease in inflammation, anemia or use of erythropoietin (epo).

**Design.** Randomized, double blind clinical trial in two arms of HD patients with 25VD deficiency and secondary hyperparathyroidism, one arm to be treated with cholecalciferol supplementation and the other with a placebo, for a period of 12 weeks.

**Population.** Patients over 18 years of age on HD for more than 3 months and levels of 25VD < 30 ng / ml and iPTH >300 ng/ml , who sign a consent form. Patients will be recruited over a period of one year. Once their consent has been obtained, iPTH and 25VD levels will be measured. Randomization will be achieved by using a table of random numbers at the pharmacy, and neither doctors nor patients will know which group they have been assigned to.

Treatment. Supplementation will consist of one 5000 IU 25VD tablet or placebo during dialysis for a period of 12 weeks.

Monthly monitoring will include: hemoglobin (g/dl), Calcium (mg/dl), Phosphorous (mg/dl), iPTH (ng/ml), epo dose (IU/kg/week), epo resistance (IU/kg/week/g Hb).

At the beginning and end of the study the following will be measured: alkaline Phosphatase (IU/ml), PCR (mg/L), 25VD (ng/ml), ferritin (ng/ml) and transferrin saturation, quality of life (SF36).

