### Specific Aims

1. Primary aim: to analyze whether it is possible to normalize levels of 25VD and reduce high levels of iPTH
2. Secondary aim: to evaluate whether it is possible to improve renal anemia in hemodialysis patients with a 12-week course of cholecalciferol
3. Secondary aim: to investigate whether cholecalciferol supplementation in HD patients is associated with hypercalcemia and hyperphosphatemia

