It will not be necessary to make changes to the dietary intake of vitamin D as dairy products, which are the main source of dietary vitamin D, are strictly limited in the diets of these patients.

Treatment: Supplementation will consist of one 5000 IU tablet of 25VD or placebo taken during dialysis for a period of 12 weeks. A nurse from the team will ensure access to the medication by being in permanent contact with the pharmacy. Monthly follow-up of the patients in the study will include evaluation of laboratory tests as well as normal clinical controls during dialysis (weight, arterial pressure and intra-dialysis hypotension events), and monthly report of dosage of erythropoietin (IU/kg/week) for the calculation of the index of resistance to erythropoietin (IU/kg/week / g of Hb).

Laboratory testing to be done monthly will include: hemoglobin (g/dl), Calcium (mg/dl), Phosphorous (mg/dl), and iPTH (ng/ml). At the beginning and at the end of the study the following will be measured: Alkaline Phosphatase (IU/ml), CRP (mg/L), ferritin (ng/ml), transferrin saturation, and 25VD (ng/ml).

The measuring of hemoglobin will be done by Siemens Healthcare Diagnostics' Advia 2120 haematological analyzer using the cyanmethemoglobin method modified without cyanide, with Siemens controls and calibrators. Dosing of vitamin D, iPTH and ferritin will be done by Siemens Healthcare Diagnostics' Advia Centaur XP analyzer using the chemiluminescence method, with BIORAD controls and Siemens calibrators.

Other measures will be taken as follows: for calcium, by the Arsenazo III endpoint method, for phosphorous, by the UV phosphomolibdate method, for alkaline phosphatase, by the kinetic technique of paranitrophenol phosphate, for iron, by the endpoint ferrocin method, for transferrin, by the immunoturbidimetric method maximized with PEG, and for reactive C Protein, by the immunoturbidimetric method maximized with latex. All of these will be done by Siemens Healthcare Diagnostics's Advia Chemistry 1800 autoanalyzer with BIORAD controls and Siemens calibrators.

Both prior to the start of the study and after it has ended, quality of life will be evaluated using SF36 auto-administered protocol.

During the 12 weeks of the study, doses of calcitriol or paracalcitol must not be modified. The study will be discontinued in those patients who present levels of calcemia  $\geq 10.5$  mg/dL on two occasions.

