#### Calculation of sample size

It was estimated, by using free access epidemiological calculator Open Epi (to be found at <http://www.openepi.com/v37/SampleSize/SSCohort.htm>), that necessary sample size to show a IPTH decrease of 20% in 35% of patients in the group treated (information we found in a previous observational study) is 102, and assuming a 15% loss of follow-up, a sample size of 120 was decided on. This size is more demanding than the 50 patients needed to demonstrate the correction of 25VD in 50% of patients.

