#### Expected Results

Primary end point: A difference in the percentage of patients normalizing levels of 25VD of at least 45% of the group treated vs placebo.

Percentage of patients of at least 30% in the group treated vs placebo presenting a decrease of 20% from previous levels of IPTH.

Secondary end point: Percentage of patients with an increase in Hb or a decrease in resistance to erythropoietin

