#### Data Analysis and Statistics

Reference demographic data will be collected related to: age, gender, race, cause of kidney disease, length of time on dialysis, presence of diabetes and use of active forms of vitamin D.

Clinical data will be taken from electronic medical records of dialysis (SISDIA): body weight, height, body mass index, monthly average of systolic and diastolic arterial pressure pre-dialysis, and monthly average percentage of inter-dialysis weight increase.

Both clinical information and laboratory data will be entered in a case report form (CRF) which will be attached as Annex 1.

Laboratory test data will be collected in Table 1 Schedule of measures.

TABLE I. SCHEDULE OF MEASURES

	Time 0	week 4	week 8	week 12	week 16
25VD					
iPTH					
Ca					
P					
Alkaline Phosphatase					
Hb					

CRP					
Ferritin					
Sat Transferrin					
SF36					
Mean SAP					
Mean DAP					
Mean inter-dialytic weight gain					
Number of hipotensive events					

The information obtained from patients' CRFs will be entered in a database which will be treated as confidential. Sensitive data will be kept confidential and patients' identity will remain anonymous during the whole procedure.

In order to ensure the quality of the information, all data entered will be checked by a second member of the research team prior to statistical analysis.

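### The calcium rule ends the study, not the tablets, in a patient, so a patient high at weeks 4 and 8 could leave with no post-baseline 25VD

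*Protocol*

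**What the plan says.** The stopping rule is in the treatment text of the protocol's POPULATION section: "The study will be discontinued in those patients who present levels of calcemia" at or above 10.5 mg/dL on two occasions. The sentence before it freezes calcitriol and paricalcitol doses for the 12 weeks. The SUMMARY gives the same threshold but omits the words that limit the rule to individual patients.

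Hemoglobin, calcium, phosphorus and iPTH are monthly. 25VD belongs to a second list, introduced in the POPULATION section by "At the beginning and at the end of the study the following will be measured" and in the SUMMARY by "At the beginning and end of the study the following will be measured".

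Expected Results names two primary endpoints. One is "A difference in the percentage of patients normalizing levels of 25VD", with an expected gap of at least 45%. The other is the percentage of patients "presenting a decrease of 20% from previous levels of IPTH", with no visit named. The SUMMARY promises intention to treat for the primary outcome. The third specific aim is "to investigate whether cholecalciferol supplementation in HD patients is associated with hypercalcemia and hyperphosphatemia".

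**The concern.** The protocol speaks of medication when it means the tablets, for example where the nurse administers them. The stopping rule instead ends the study in the patient. On the plain reading the patient leaves, and nothing in the document requires a sample at exit or at week 12.

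For iPTH the damage is partial, because the week-4 and week-8 values exist. For 25VD, on the prose schedule, no post-baseline value exists at all. An analysis plan can choose how to treat a missing value, but it cannot supply blood that was never drawn. Sampling after stopping is trial conduct and has to be settled in the protocol.

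The loss would also not be random. Its trigger is high calcium, which the third aim treats as a possible effect of cholecalciferol, so losses could differ by arm. An intention-to-treat analysis is meant to protect against exactly that.

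**Working it through.** **Which patients are exposed.** Corrected calcemia of 10.5 or more in the 2 months before recruitment is an exclusion. On scheduled visits, then, the two high values are post-baseline and the earliest pair is weeks 4 and 8. If the second high value comes at week 12, the final samples are due at that visit and nothing is lost. The exposed patient is the one who is high at both week 4 and week 8.

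| Measure | Post-baseline values if the patient leaves at week 8 (prose schedule) |
|---|---|
| Calcium | weeks 4 and 8, so the event itself is recorded |
| iPTH | weeks 4 and 8; week 12 lost |
| 25VD | none, unless an exit sample is drawn |

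**The plan's own sample size.** Assume a two-sided 5% test, 80% power, 1:1 allocation, a control rate of 10% and the continuity correction; the document states none of these.
- iPTH, 35% vs 10%: 51 per arm, total 102, as stated. Allowing for 15% loss: 102 / 0.85 = 120, as stated.
- 25VD, 50% vs 10%: 25 per arm, total 50, as stated.

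The concern changes none of these figures.

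**How many patients.** The document gives no rate of high calcium, so p, the share of readings at or above 10.5, is an assumption. With 60 treated patients (half of 120), the expected number high at both visits is 60p² if visits are independent and 60p if a high value always persists.

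| p | 60p² | 60p |
|---|---|---|
| 2% | 0.02 | 1.2 |
| 5% | 0.15 | 3 |
| 10% | 0.6 | 6 |

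Each lost patient leaves 1/60 = 1.7 percentage points of that arm's week-12 responder rate undetermined.

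**Effect on 25VD.** The treated rate of 50% comes from the sample-size section ("demonstrate the correction of 25VD in 50% of patients"). The control rate is assumed to be 5% or 10%. Take 6 treated patients lost, none on placebo, all would-be normalizers and all counted as failures. The treated rate becomes 0.50 − 6/60 = 0.40. Exact power of the uncorrected chi-square test, 60 per arm:
- control 5%: from above 99.9% to 99.9%
- control 10%: from 99.9% to about 98%

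The test is hardly affected. The estimated difference shrinks by up to 10 points, for example from 45 to 35 with a control rate of 5%.

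**Effect on iPTH.** True rates 35% vs an assumed 10%, 60 per arm, with the retained week-4 and week-8 values ignored. With none lost, exact power is 92.7%. With k treated patients lost, of whom a fraction q would have responded:
- completers: treated rate (0.35 − kq/60) / (1 − k/60), with 60 − k vs 60 patients
- lost counted as failures: treated rate 0.35 − kq/60, with 60 vs 60 patients

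| k | Completers, q = 1 / 0.35 / 0 | Lost as failures, q = 1 / 0.35 / 0 |
|---|---|---|
| 1 | 90.6 / 92.6 / 93.5% | 89.6 / 91.7 / 92.7% |
| 3 | 84.6 / 92.2 / 94.8% | 80.2 / 89.4 / 92.7% |
| 6 | 70.9 / 91.6 / 96.5% | 58.5 / 85.0 / 92.7% |

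**Losses in both arms.** Placebo patients may also take calcitriol or paricalcitol, so nil placebo loss is only an assumption. If 6 of 60 are lost in each arm, respond at their arm's average rate and are counted as failures, the rates are 0.35 × 0.9 = 0.315 and 0.10 × 0.9 = 0.09, and the same exact power is 88.8%.

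**The case against.** The strongest reply is that the wording is ambiguous, not wrong. If the study ends in a patient, the end of the study for that patient may be that moment, and the final 25VD would then be drawn at exit. That reading is possible, but no text states it, and a site following the protocol would have no instruction to draw the sample. It would also still leave no week-12 value.

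A second reply is that ending the study may be deliberate, because it frees the patient from the adjacent freeze on calcitriol and paricalcitol. This stands. A change that stopped only the tablet could leave a twice-hypercalcemic patient on a fixed dose of active vitamin D, so the freeze must be lifted in the same sentence.

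A third is that "TABLE I. SCHEDULE OF MEASURES" might show more samples. It has a 25VD row and columns to week 16, but its cell marks are not readable in the text at hand. It can neither rescue nor worsen the point.

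A fourth is that the 15% follow-up allowance (120 − 102 = 18 patients) more than covers the numbers. It does cover numbers, but not a loss that depends on treatment.

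A reader might infer from the low iPTH figures (58.5% and 70.9%) that power is at risk. The documents do not support that. Those figures need 10% of readings high, perfect persistence, every lost patient a would-be responder and no placebo losses, and they ignore the iPTH values at weeks 4 and 8. With average response among 6 lost, power is 91.6% (completers) or 85.0% (counted as failures).

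**Conclusion.** The concern holds as a minor one. Followed as written, the rule can remove a patient's only post-baseline 25VD and the week-12 iPTH for a possibly treatment-related reason, which sits badly with the promised intention-to-treat analysis. This rests on the plain reading of the rule and on the prose sampling schedule.

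The number affected is unknown and probably small, since recent high calcium is excluded at entry. The direction of bias is unknown and the effect on power is likely slight. In the extreme case the 25VD difference is understated by up to 10 points, while its power stays at about 98% or more.

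Two further inferences are not supported. Safety information on the event is not lost, because both high readings are already recorded; only the later course would be missing. Nor does the looser SUMMARY sentence show an intention to stop the whole trial, because the fuller text limits the rule to the patients concerned.

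**What to change.** Replace the stopping sentence in the treatment text with wording to this effect, and use the same per-patient wording in the SUMMARY:

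> Study medication is stopped in a patient with calcemia ≥10.5 mg/dL on two occasions; from then on calcitriol or paricalcitol may be adjusted as clinically needed and any change is recorded. 25VD and iPTH are drawn at discontinuation, and the scheduled calcium, iPTH and 25VD samples continue through week 12; the patient is analysed in the assigned arm.

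The cost is a wording amendment and one additional 25VD test, plus an iPTH test where none is already due, in the few patients who stop early. These patients attend dialysis anyway, and sample size and duration do not change. The downside is that their week-12 values reflect a shortened course and possibly changed active vitamin D doses, which an intention-to-treat analysis accepts.

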During the study, doses of calcitriol or paricalcitol will not be modified.

The study will be discontinued if calcemia  $\geq$  10.5 mg/dL is detected on two occasions.

Size of sample is estimated at 120 patients for a iPTH decrease of 20% in 35% of patients in group treated (assuming 15% follow-up losses). Analysis will be done for Intention to treat for the primary outcome.

Ethical aspects: Authorization has been obtained from the Ethics Committee of the institution as regards Good Clinical Practices, Helsinki Declaration and national regulations. The test will be registered with Cochrane and the Ministry of Public Health.

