### POPULATION

Criteria for inclusion: Age 18 or over, signed informed consent form, CKD with regular dialysis treatment for at least 3 months, levels of 25VD < 30 ng / ml and iPTH >300 ng/ml, stable doses of calcitriol or paricalcitol over the last 30 days.

Criteria for exclusion: Congestive heart failure class III or IV or unstable angina

or myocardial infarction or stroke during the previous 3 months, active malignant neoplasm, use of any trial medication, life expectancy lower than 6 months, corrected calcemia  $\geq 10.5$  in the 2 months prior to recruitment, intake of cholecalciferol or ergocalciferol in the 2 months prior to recruitment, prospective move to another city or transfer to PD in the following 6 months.

Patient recruitment. Patients will be recruited over a one-year period when the study will be explained to them, and samples will be taken to assess whether they fulfill the criteria for inclusion in the trial. Once iPTH and 25VD testing has taken place, eligible participants will be requested to sign an informed consent form, and will be told that they will be treated either with cholecalciferol or a placebo. They will be assigned to one of the arms using a table of random numbers at the pharmacy of the institution, stratified in two subgroups according to vitamin D levels: below 15 ng/ml or between 15 and 29.

Randomization. Once approval has been received from the Ethics in Research Committee and the consent form has been signed, patients will be assigned to one arm by using a table of random numbers, according to a number from 0 to 9 which will be drawn at random at the time the patient is included. For purposes of randomization, one fixed number will be skipped from the starting point which is only known by the person who does the randomization at the pharmacy, using a starting point selected initially on the table. Notification of the arm allocated will arrive in sealed envelopes with the medication to be taken (either cholecalciferol or the placebo) which will be administered orally during dialysis.

The laboratory that prepares the medication and the placebo will send them to the pharmacy labelled as medication A and B. Then the pharmacy of the

institution will send the tablets to the patient, neither the doctors nor the patient knowing what arm he has been assigned to. The medication will be administered by the nurse during dialysis.

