## Security Measures

Patients will be evaluated for early detection of side effects, particularly in relation to increases in calcemia and fosfatemia. Both calcium and phosphorous will be measured monthly.

If it were necessary to open the blinding, it will be requested from the person in charge of assigning the medication at the pharmacy.

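### The two-reading calcium stop has no timed repeat, so on the monthly draws alone a sustained rise first seen at week 8 is confirmed only when dosing has ended

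*Protocol*

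**What the plan says.** The individual stopping rule is in the Treatment text of the Protocol's Methods (under POPULATION): "The study will be discontinued in those patients who present levels of calcemia" at or above 10.5 "mg/dL on two occasions". The Summary has a shorter form, beginning "The study will be discontinued if calcemia", with the same threshold and the same two occasions. The Methods wording makes clear that the rule applies to the patient, and it is read that way here.

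On monitoring, Security Measures says "Patients will be evaluated for early detection of side effects, particularly in relation to increases in calcemia and fosfatemia", and then "Both calcium and phosphorous will be measured monthly". Table I lists calcium as a row and has columns at Time 0 and weeks 4, 8, 12 and 16. Its cells are blank in the text at hand, but the monthly frequency is stated in words.

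Three other statements bear on the point:

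- Active vitamin D is frozen: "During the 12 weeks of the study, doses of calcitriol or paracalcitol must not be modified". No exception for a high calcium is given.
- Raised calcium before entry is an exclusion. The list includes "life expectancy lower than 6 months, corrected calcemia" at or above 10.5 in the 2 months before recruitment.
- Hypercalcemia is a secondary aim under Specific Aims: "to investigate whether cholecalciferol supplementation in HD patients is associated with hypercalcemia and hyperphosphatemia".

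No section states when the second reading is due, provides for a repeat, or names an action after a first high value.

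**The concern.** A rule that needs two high values protects a patient only as fast as the second value arrives. With monthly sampling and a 12-week course there are few chances for a second value while treatment can still be stopped. A site that follows the schedule literally would leave a patient with a sustained rise on study drug for another 4 weeks after the first high reading, with any calcitriol or paricalcitol held at its current dose. That sits poorly with the early-detection purpose in Security Measures, and the high calcium count is the only individual stopping criterion the Protocol states. The tablet is given by a nurse at dialysis, so a repeat could be drawn at a session the patient already attends.

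**Working it through.** **Inputs.** Treatment lasts 12 weeks (Treatment text). Calcium is drawn monthly (Treatment text, Security Measures), taken as weeks 4, 8, 12 and 16 from the Table I columns. The rule needs two values of 10.5 mg/dL or more. Time 0 is assumed below 10.5, which fits the exclusion criterion. The plan states no figure of its own to reproduce.

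**Scheduled draws only, sustained rise.** Dosing after the first high value = week of second high (at most 12) − week of first high. Course left to stop = 12 − week of second high, not below 0.

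| First high | Second high | Dosing after first high | Course left to stop |
|---|---|---|---|
| week 4 | week 8 | 8 − 4 = 4 weeks | 12 − 8 = 4 weeks |
| week 8 | week 12 | 12 − 8 = 4 weeks | 12 − 12 = 0 weeks |
| week 12 | week 16, if drawn | 0 weeks | 0 weeks |

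A patient high at weeks 4 and 12 but normal at week 8 also reaches the second occasion at week 12, with 0 weeks left. So only the pattern high at both weeks 4 and 8 shortens the course. Four weeks is 4/12 = 33% of the course.

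**With a repeat d weeks after the first high value.** The interval d is an assumption. The repeat is high because the rise is sustained.

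- d = 1: stop at week 5 or 9. Dosing after the first high value is 1 week (1/12 = 8%). Course left to stop is 12 − 5 = 7 or 12 − 9 = 3 weeks. Dosing avoided compared with the schedule: 7 − 4 = 3 or 3 − 0 = 3 weeks.
- d = 2: stop at week 6 or 10. Dosing after the first high value is 2 weeks (2/12 = 17%). Course left to stop is 6 or 2 weeks. Dosing avoided: 6 − 4 = 2 or 2 − 0 = 2 weeks.

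**Sensitivity to Time 0.** The exclusion refers to corrected calcium and the stopping rule to calcemia without that word, so a high Time 0 value is not fully ruled out. High at Time 0 and week 4 would stop the patient at week 4, which is 12 − 4 = 8 weeks early. High at Time 0 and week 8 would stop at week 8, which is 4 weeks early. The result for a patient normal at Time 0 and week 4 does not change.

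**The case against.** The strongest reply is that this argues from silence. The rule says two occasions; it does not say two scheduled draws. A clinician who sees a high result in a patient attending dialysis can redraw at an upcoming session and still comply. That stands. A reader might infer that the Protocol prevents early confirmation, or obliges four more weeks of dosing after a high result. The text supports neither. What remains is that the repeat is left to discretion, so patients with the same calcium course could be stopped weeks apart.

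The second reply is that the benefit cannot be sized. The weeks avoided are simply 4 − d for an assumed d and a sustained rise, and no hypercalcemia rate is given. The Introduction also describes the drug as having few side effects. This stands, and it limits the priority. In addition, weeks of dosing avoided are not weeks of exposure avoided: the Protocol puts the 25VD half-life at about 2 weeks or more, so levels fall slowly after stopping. That can be read two ways. It weakens the gain from stopping at week 9 instead of 12, and it is also a reason not to confirm late.

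The third reply is that the remedy is not neutral. On the schedule the two readings are at least 4 weeks apart; with a prompt repeat they may be 1 week apart. A patient high at weeks 4 and 5 but normal at weeks 8 and 12 would be stopped under the remedy and not under the scheduled draws. Stopped patients also have no on-treatment calcium at later visits, which touches the hypercalcemia aim. Both points stand and belong in the cost.

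The freeze on active vitamin D adds less than it may seem. Its use is recorded as a baseline characteristic, which suggests that not every patient takes it, and no separate gain is claimed for changing it.

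**Conclusion.** The point holds in a limited form. If the scheduled draws alone are used and Time 0 is below 10.5, the stop shortens the course only for patients high at both weeks 4 and 8, by 4 weeks. A sustained rise first seen at week 8 is confirmed when dosing has ended. A timed repeat at 1 or 2 weeks (assumed) would avoid about 3 or 2 weeks of dosing for a sustained rise, whether it is first seen at week 4 or week 8. No saving is claimed for a patient high at weeks 4 and 12 but normal between.

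A reader might go further and conclude that the stopping rule does not work, or that a known number of patients is left at risk. Neither follows: the rule does act for a rise present by week 4, an earlier redraw is allowed, and without a hypercalcemia rate no count can be given. This is a cheap improvement of modest priority.

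**What to change.** In the Summary, the Treatment text and Security Measures, state that any on-treatment calcium of 10.5 mg/dL or more is repeated at an upcoming dialysis session, for example within 1 week with the interval set by the investigators, and that this repeat counts as the second occasion. Keep the threshold and the need for two readings, so a single isolated value still stops no one. Continue the scheduled calcium and iPTH draws after discontinuation, and compare hypercalcemia between arms on scheduled draws only, so that repeats do not add to the count. Optionally, say that the calcitriol and paricalcitol freeze ends when a patient is discontinued for high calcium.

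**Cost.** Wording in three places, and at most one extra calcium test per patient, because any later high reading is itself the second occasion. The ceiling is 120 tests. If 5% to 15% of patients have a first high value at week 4 or 8 (assumed), it is 120 × 0.05 = 6 to 120 × 0.15 = 18 tests.

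The rule becomes somewhat stricter: short-lived rises that would be normal at the next monthly draw may now stop a patient, and some on-treatment calcium values are lost. Each active-arm patient who loses the 20% iPTH response this way lowers that arm's responder share by 1/60 = 1.7 percentage points (120/2 = 60, equal arms assumed), against the 30% set under Expected Results. How many would do so cannot be estimated from the document.
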